4.6 Duration of Follow Up

Patients will be enrolled in the study for 6 weeks. They will be followed in clinic every 2 weeks with the option for remote visits instead of in-person visits by submitting the required documentation and photography to the study team ahead of the remote visit for review. The

NU Study Number: JNC06142016 Other Study Numbers: STU00203631; NU 16D05

remote visit will happen using telephone to review the protocol, answer questions and concerns, and review diaries, questionnaires, and AEs.

They will not be followed up after the final visit during the 6th week, when they will terminate the drug regimen.

4.7 Removal of Subjects from Study Treatment and/or Study as a Whole

Patients can be taken off the study treatment and/or study as a whole at any time at their own request, or they may be withdrawn at the discretion of the investigator for safety, behavioral or administrative reasons. The reason(s) for discontinuation must be clearly documented on the appropriate eCRF and may include:

NU Study Number: JNC06142016 Other Study Numbers: STU00203631; NU 16D05

- Patient voluntarily withdraws from treatment (follow-up permitted)
- Patient withdraws consent (no follow-up permitted)
- Patient is unable to comply with protocol requirements
- Patient demonstrates disease progression
- Patient experiences unacceptable toxicity as determined by either the patient's physician or by the patient himself
- Treating physician determines that continuation on the study would not be in the patient's best interest
- Patient becomes pregnant
- Patient develops a second malignancy that requires treatment which would interfere with this study
- Patient becomes lost to follow-up (LTF)

5.0 STUDY PROCEDURES

	Screening	On Treatment		
Time Period	Baseline	Week 2	Week 4	Week 6
Assessment or Activity				
Informed Consent	×			
Obtain history ¹	×			
Complete skin exam ²	Х	Х	Х	Х
Standardized digital photos of face, chest, and back	Х	X	Х	Х
FACT-EGFRI-18 Questionnaire	Х	Х	Х	Х
Assess for adverse side effects		X	X	Х
Review of patient diary		X	X	Х
Application of topical triamcinolone 0.1% cream	Х	X	X	_
Nasal Swab ³	×			Х

NU Study Number: JNC06142016 Other Study Numbers: STU00203631; NU 16D05

6.0 ENDPOINT ASSESSMENT

6.1 Definitions

A grade 2 rash is defined in Table 1 (p. 5) as papules and/or pustules covering 10-30% body surface area (BSA), which may or may not be associated with symptoms of pruritus or tenderness; associated with psychosocial impact; limiting instrumental activities of daily living (iADL).

6.2 Primary Endpoint

The study endpoint is defined as the percentage of patients who develop a grade 2 or greater rash between the control group as compared to the case group of preemptive treatment with topical steroids (triamcinolone 0.1% cream for application to face, chest and back) when administered concomitantly for 6 weeks with erlotinib, cetuximab, panitumumab, afatinib or osimertinib to prevent papulopustular eruptions.

6.3 Secondary Endpoints

- **6.3.1** The difference in maximum severity of rash between the preemptive treatment group and the reactive treatment group
- **6.3.2** The difference in change in quality of life due to rash between the two treatment groups.
- **6.3.3** The difference in adherence to chemotherapy between the two treatment groups.
- **6.3.4** The association of baseline nasal swab cultures and development of rash or rash severity.

7.0 ADVERSE EVENTS

This study will be conducted in compliance with the Data Safety Monitoring Plan (DSMP) of the Robert H. Lurie Comprehensive Cancer Center of Northwestern. The level of risk attributed to this study requires moderate intensity monitoring, as outlined in the DSMP. In addition, the study will abide by all safety reporting regulations, as set forth in the Code of Federal Regulations.

7.1 Adverse Event Monitoring

Adverse event data collection and reporting, which are required as part of every clinical trial, are done to ensure the safety of subjects enrolled in the studies as well as those

¹Includes demographic data, medical history, medication list, history of drug reactions, personal and family history of acne/rosacea

²Includes baseline count of any macules, papules, or pustules present on face, chest, and back at baseline.

³ A nasal swab will be optional for the patient at the first and last treatment and at any time a rash with pustules develops. If the optional nasal swab is positive for bacterial colonization, this will be treated per standard of care.

who will enroll in future studies using similar agents. Adverse events are reported in a routine manner at scheduled times during a trial (see Section 5 for timepoints). In addition, certain adverse events must be reported in an expedited manner to allow for optimal monitoring and patient safety and care.

All patients experiencing an adverse event, regardless of its relationship to study drug, will be followed until:

- the adverse event resolves or the symptoms or signs that constitute the adverse event return to baseline;
- any abnormal laboratory values have returned to baseline;
- there is a satisfactory explanation other than the study drug for the changes observed; or
- death.

7.2 Definitions & Descriptions

7.2.1 Adverse Event

An adverse event (AE) is any untoward medical occurrence in a patient receiving study treatment and which does not necessarily have a causal relationship with this treatment. Because AEs associated with EGFR- inhibitor treatment are monitored by the treating oncology physician, for the purposes of this study, only AEs that were possibly, probably, or definitely related to triamcinolone 0.1% cream will be collected, including those symptoms listed in section 8.1.9 will be reported. An AE can therefore be any unfavorable and unintended sign (including an abnormal laboratory finding), symptom, or disease temporally associated with the use of an experimental intervention, whether or not related to the intervention.

Recording of AEs should be done in a concise manner using standard, acceptable medical terms. In general, AEs are not procedures or measurements, but should reflect the reason for the procedure or the diagnosis based on the abnormal measurement. Preexisting conditions that worsen in severity or frequency during the study should also be recorded (a preexisting condition that does not worsen is not an AE). Further, a procedure or surgery is not an AE; rather, the event leading to the procedure or surgery is considered an AE.

If a specific medical diagnosis has been made, that diagnosis or syndrome should be recorded as the AE whenever possible. However, a complete description of the signs, symptoms and investigations which led to the diagnosis should be provided. For example, if clinically significant elevations of liver function tests are known to be secondary to hepatitis, "hepatitis" and not "elevated liver function tests" should be recorded. If the cause is not known, the abnormal test or finding should be recorded as an AE, using appropriate medical terminology (e/g/ thrombocytopenia, peripheral edema, QT prolongation).

7.2.2 Severity of AEs

All adverse events will be graded according to the NCI Common Terminology Criteria for Adverse Events (CTCAE) version 4.03. The CTCAE v4 is available at http://ctep.cancer.gov/reporting/ctc.html

If no CTCAE grading is available, the severity of an AE is graded as follows:

- Mild (grade 1): the event causes discomfort without disruption of normal daily activities.
- Moderate (grade 2): the event causes discomfort that affects normal daily activities.

- Severe (grade 3): the event makes the patient unable to perform normal daily activities or significantly affects his/her clinical status.
- Life-threatening (grade 4): the patient was at risk of death at the time of the event.
- Fatal (grade 5): the event caused death.

7.2.3 Serious Adverse Events (SAEs)

All SAEs, regardless of attribution, occurring from time of signed informed consent, through 30 days after the last administration of study drug, must be reported upon discovery or occurrence.

An SAE is defined in regulatory terminology as any untoward medical occurrence that:

- Results in death.
 - If death results from (progression of) the disease, the disease should be reported as event (SAE) itself.
- Is life-threatening.
 - The patient was at risk of death at the time of the event; it does not refer to an event that hypothetically might have caused death if it were more severe.
- Requires in-patient hospitalization or prolongation of existing hospitalization for ≥ 24 hours.
- Results in persistent or significant disability or incapacity.
- Is a congenital anomaly/birth defect.
- Is an important medical event.

Any event that does not meet the above criteria, but that in the judgment of the investigator jeopardizes the patient, may be considered for reporting as a serious adverse event. The event may require medical or surgical intervention to prevent one of the outcomes listed in the definition of "Serious Adverse Event".

For example: allergic bronchospasm requiring intensive treatment in an emergency room or at home; convulsions that may not result in hospitalization; development of drug abuse or drug dependency.

7.2.4 Unanticipated Problems Involving Risks to Subject or Others

A UPIRSO is a type of SAE that includes events that meet ALL of the following criteria:

- Is unanticipated in terms of nature, severity, or frequency
- Places the research subject or others at a different or greater risk of harm
- Is deemed to be at least possibly related to participation in the study.

7.3 Adverse Event Reporting

7.3.1 Routine Reporting

All routine adverse events that are determined to be possibly, probably, or definitely related to study treatment should be reported on the adverse event (AE) Case Report Form (CRF) within NOTIS Routine AEs will be reviewed by the Data Monitoring Committee (DMC) according to the study's phase and risk level, as outlined in the DSMP.

7.3.2 Determining if Expedited Reporting is Required

This includes all events that occur within 30 days of the last dose of protocol treatment. Any event that occurs more than 30 days after the last dose of

treatment and is attributed (possibly, probably, or definitely) to the agent(s) must also be reported accordingly.

- 1) Identify the type of adverse event using the NCI CTCAE v 4.03.
- 2) Grade the adverse event using the NCI CTCAE v4.03.
- 3) Determine whether the adverse event is related to the protocol therapy. Attribution categories are as follows:
 - Definite: AE is clearly related to the study treatment.
 - Probable: AE is likely related to the study treatment.
 - Possible: AE may be related to the study treatment.
 - Unlikely: AE not likely to be related to the study treatment.
 - Unrelated: AE is clearly NOT related to the study treatment.
- Determine the prior experience of the adverse event.

 Expected events are those that have been previously identified as resulting from administration of the agent. An adverse event is considered unexpected, for expedited reporting purposes only, when either the type of event or the severity of the event is not listed in:
 - the current protocol
 - the drug package insert
 - the current Investigator's Brochure

7.3.3 Expedited Reporting of SAEs/Other Events

7.3.3.1 Reporting to the Northwestern University QAM/DMC

All SAEs must be reported to the assigned QAM within 24 hours of becoming aware of the event. Completion of the NU CRO SAE Form, provided as a separate document, is required.

The completed form should assess whether or not the event qualifies as a UPIRSO. The report should also include:

- Protocol description and number(s)
- The patient's identification number
- A description of the event, severity, treatment, and outcome (if known)
- Supportive laboratory results and diagnostics
- The hospital discharge summary (ifavailable/applicable)

All SAEs will be reported to, and reviewed by, the DMC at their next meeting.

7.3.3.2 Reporting to the Northwestern University IRB

The following information pertains to the responsibilities of the lead site (Northwestern University). Additional participating sites should follow their local IRB guidelines for reporting to their local IRBs.

- Any death of an NU subject that is unanticipated in nature and at least possibly related to study participation will be promptly reported to the NU IRB within 24 hours of notification.
- Any death of an NU subject that is actively on study treatment (regardless of whether or not the event is possibly related to study treatment)
- Any death of a non-NU subject that is unanticipated and at least possibly related and any other UPIRSOs will be reported to the NU IRB within 5 working days of notification.
- All other deaths of NU subjects not previously reported, other non-NU subject deaths that were unanticipated and unrelated, and any

NU Study Number: JNC06142016 Other Study Numbers: STU00203631; NU 16D05

other SAEs that were not previously reported as UPIRSOs will be reported to the NU IRB at the time of annual continuing review.

8.0 DRUG INFORMATION

- 8.1 Triamcinolone 0.1% topical cream
 - 8.1.1 Other names: Aristocort, Aristogel, Flutex, Kenalog, Triacet, Triacort, Triatex, Triderm, Trymex
 - 8.1.2 Classification: topical steroid
 - **8.1.3 Mode of action:** Induce inhibitory proteins to the production of phospholipase A2, preventing the release of arachidonic acid in the inflammatory pathway.
 - **8.1.4** Storage and stability: store away from moisture and light, at room temperature.

8.1.5 Protocol dose specifics

Application of triamcinolone 0.1% cream to 25% BSA will result in subpharmacological dosing that mimics physiologic equivalent of corticosteroids. Topical application of triamcinolone 0.1% cream is not likely to result in significant systemic absorption that will produce hypothalamic-pituitary-adrenal axis suppression and therefore, will not pose a risk for glucocorticosteroid insufficiency after withdrawal of treatment.

8.1.6 Preparation

The patient will apply approximately 5 grams total (1 teaspoon) to the face, chest, and back twice a day.

8.1.7 Route of administration for this study: topical cream application

8.1.8 Availability & Supply

This drug will be provided by the Northwestern Research Pharmacy, and will be stored at [name] in a locked storage room of the Dermatology Department. The drug will be stored with the investigational drug log.

8.1.9 Side effects

- Blistering, burning, crusting, dryness, or flaking of the skin
- Thinning of the skin with easy bruising
- Itching, scaling, severe redness of the skin
- Redness and scaling around the mouth
- Acne or pimples
- Burning and itching of the skin with blisters
- Burning, itching, and pain in hairy areas, or pus at root ofhair
- Increased hair growth on forehead, back, arms, legs
- Lightening of normal skin color
- · Lightening of treated areas of dark skin
- Reddish purple lines on arms, face, legs, trunk, or groin
- Softening of the skin

9.0 STATISTICAL CONSIDERATIONS

9.1 Study Design/Study Endpoints

This study is a randomized control trial with a control arm and a treatment arm. The primary study endpoint is defined as the percentage of patients developing a grade 2 rash or greater.

9.2 Sample Size and Accrual

A total of 80 patients will be enrolled in the study. Assuming a low 3% lost to follow-up rate, we will aim for a sample size of 84 patients (42 patients per treatment group), which will provide 80% power to detect a difference in rash incidence of 30% between the steroid arm and control group (i.e. 45% in the steroid arm versus 75% in the control group).

9.3 Data Analyses Plans

The primary objective will be to assess and compare the incidence of rash in patients treated preemptively with topical steroids and control patients.

Proportions experiencing EGFRI-induced papulopustular eruption (any severity) by 6 weeks will be estimated and compared using the Mantel-Haenszel Chi-Square test to account for the stratification factor in the randomization procedure. A test for homogeneity will be performed to assess the adequacy of a common odds ratio (OR). Results will be summarized using an OR and 95% confidence interval. Supportive analysis will use a generalized estimating equations (GEE) approach, which will allow modeling of the proportion of patients with rash over time. Fixed factors for treatment group, time and the treatment group by time interaction will evaluate time differences in the proportion of patients with rash between the two treatment arms while accommodating repeated measures over time.

The secondary objective, maximum grade severity during the 6-week study period will be tabulated by treatment group and compared using the Cochrane Armitage test for trend.

Secondary endpoints will also include comparisons across the study arms to assess changes in quality-of-life scores from baseline, as measured by the FACT-EGFRI-18 questionnaire. FACT-EGFRI-18 scores will be presented as the median percentage from baseline. Scores at 6 weeks will be compared using the nonparametric Van Elteren test, which combines stratum-specific Wilcoxon Rank-Sum statistics with weights inversely proportional to stratum sizes. Differences in adherence to chemotherapy treatment over the 6 weeks will be compared across the two study arms using the Mantel-Haenszel Chi-Square test. The incidence of adverse events will also be compared across treatment arms with a Fisher exact test.

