1.2 Intervention Background & Overview

Oral antibiotics

The first published randomized controlled clinical trial that prospectively evaluated a systemic therapy for the EGFRI-induced papulopustular eruption investigated the use of oral minocycline (100 mg daily) versus placebo for 8 weeks, beginning on the same day as the initiation of cetuximab therapy (n = 48 patients; 24 in each arm). ²² Patients also received topical tazarotene daily to one side of the face. Overall the number of lesions increased rapidly during the first 4 weeks of therapy and then stabilized by week 8. Patients treated with minocycline had significantly lower log lesion counts than those in the placebo group from weeks 1 through 4 (p = 0.005). This difference was apparent by week 1, peaked at weeks 2 and 4, and then tapered by week 8. At week 4, there were a lower proportion of patients in the minocycline arm who reported moderate to severe itch than in the placebo arm. Additionally, there was a trend toward a lower frequency of a moderate to severe rash in patients in the minocycline arm (20%) compared with those receiving placebo (42%) (p = 0.13). Tazarotene did not have any significant benefit and was associated with significant irritation. While there was no statistically significant difference in moderate to severe rashes between the minocycline and placebo arms, possible explanations include a sub-therapeutic dose of minocycline. In acne vulgaris, minocycline is frequently used at a dosage of 100 mg twice daily to provide maximal benefit.²³

Version Date: 01-25-2021 8

In a second placebo-controlled trial conducted by the North Central Cancer Treatment Group (NCCTG), 9 this phase III trial examined 61 patients who had begun treatment with an EGFRI within 7 days of study entry and had not yet developed rash. The patients were randomized to oral tetracycline (500 mg twice daily) versus placebo for 4 weeks. There was no difference in rash incidence at 4 weeks; however, tetracycline lessened the rash severity. Seventeen percent of tetracycline-treated patients had a grade 2 or worse rash at 4 weeks compared with 55% of placebo-treated patients (p = 0.04). Additionally, the tetracycline arm was associated with improvements in pruritus according to Skindex-16 scores. (Skindex-16 is a previously validated questionnaire used as a dermatologic quality-of-life instrument relevant to rash development and its implications on symptoms, emotions, and functioning.²⁴)

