Most recently, a phase II Skin Toxicity Evaluation Protocol with Panitumumab (STEPP) trial investigated the effectiveness of oral doxycycline (100 mg twice daily) by randomizing 95 patients with metastatic colorectal cancer to either: (1) preemptive therapy (started 24 hours prior to initiation of panitumumab plus irinotecan or FOLFIRI [leucovorin, 5-fluorouracil, irinotecan], and continued daily through week 6); or (2) reactive therapy (started when symptoms of dermatologic toxicity first appeared). In addition to the doxycycline, the treatment regimen consisted of topical hydrocortisone 1% cream twice daily, sunscreen when going outdoors, and moisturizer to areas of xerosis. At week 6, preemptive treatment reduced the incidence rate of grade 2 or greater skin toxicities by over 50% when compared to reactive treatment. The incidence of grade 2 or greater skin toxicities during the 6-week skin treatment period was 29% and 62% for the preemptive and reactive groups, respectively. Additionally, the time to severe skin toxicity was significantly delayed by preemptive skin treatment. At 6 weeks, the event- (grade 2 or greater skin toxicity) free probabilities were 70% and 38% for the preemptive and reactive arms, respectively.

Overall, two of these three controlled studies suggest that the tetracycline derivatives can lessen the severity, and possibly prevent, EGFRI-induced papulopustular eruptions. The beneficial effects of tetracyclines can be attributed to their anti-inflammatory effects, as well as their tissue-protective properties, such as their inhibition of neutrophil and eosinophil chemotaxis²⁵. In addition, tetracyclines may have antineoplastic properties. In *in vitro* studies, doxycycline has been shown to have anti-angiogenic properties and induces apoptosis in colorectal cancer cells.²⁶ Thus, it is theoretical that doxycycline may have beneficial effects against tumor activity.

Currently, the standard of care according to current interdisciplinary guidelines for management of the EGFRI-associated papulopustular eruption includes initiation of either oral doxycyline 100 mg twice daily or oral minocycline 100 mg twice daily at the onset of grade 2 or greater severity of rash. ¹⁹ The most common side effects associated with the tetracycline antibiotics are nausea, vomiting, and diarrhea. Often times, these gastrointestinal-related side effects may lead to cessation of treatment with these antibiotics.

Topical Steroids

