2.0 OBJECTIVES & ENDPOINTS

2.1 Primary Objective & Endpoint

To assess the difference in percentage of participants who develop a grade 2 or greater rash in the control group as compared to the case group of preemptive treatment with topical steroids (triamcinolone 0.1% cream for application to face, chest and back) when administered concomitantly for 6 weeks with erlotinib, cetuximab, panitumumab, afatinib or osimertinib to prevent papulopustular eruptions.

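### The primary endpoint is rash of grade 2 or higher, but the primary test is specified for rash of any severity and the power statement names no grade

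*Combined protocol and SAP*

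**What the plan says.** Three sections agree on the primary endpoint. Section 2.1 sets the objective as the "difference in percentage of participants who develop a grade 2 or greater rash". Section 6.2 states: "The study endpoint is defined as the percentage of patients who develop a grade 2 or greater rash". Section 9.1, which opens the statistical chapter, repeats it: "The primary study endpoint is defined as the percentage of patients developing a grade 2 rash or greater". The only definition given in Section 6.1 is that of a grade 2 rash under CTCAE v4.03.

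Section 9.3 departs from this. It restates the primary objective as a comparison of rash incidence, with no grade, and then specifies: "Proportions experiencing EGFRI-induced papulopustular eruption (any severity) by 6 weeks will be estimated and compared using the Mantel-Haenszel Chi-Square test". The homogeneity test, the odds ratio and its 95% confidence interval belong to that same analysis. The supportive GEE model is for the proportion of patients with rash, again with no grade.

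Section 9.2 claims "80% power to detect a difference in rash incidence of 30% between the steroid arm and control group", with 75% in the control arm and 45% in the steroid arm. It does not say which grade those rates describe.

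The only other analysis in Section 9.3 that uses grade is a secondary trend test on maximum severity.

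**The concern.** An analyst who follows Section 9.3 literally never tests the endpoint that Sections 2.1, 6.2 and 9.1 call primary. The parenthesis in Section 9.3 says any severity, so the sentence cannot be read as loose shorthand for grade 2 or higher.

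The difference can change the result. Section 1.2 describes a placebo-controlled tetracycline trial in which "There was no difference in rash incidence at 4 weeks; however, tetracycline lessened the rash severity", with rash of grade 2 or worse in 17% versus 55%. If the steroid makes the rash milder without preventing it, the primary test as written would miss the effect. If it prevents only grade 1 rash, the test would report success with nothing gained on the defined endpoint. With both definitions in the plan, either could be chosen after the data are seen.

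The power statement has a related gap. The 75% control rate lies inside the any-grade range quoted in Section 1.1 (45-90%). It lies above every moderate-to-severe or grade 2+ figure the protocol cites for patients without preemptive treatment. It may therefore be an any-grade rate.

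**Working it through.** **1. The plan's own figure.** Inputs: control 0.75 and steroid 0.45 (Section 9.2), two-sided 5% (Study Summary), 80% power, 1:1 allocation, 84 patients with 3% loss.

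n per arm = [1.96 × s0 + 0.8416 × s1]² / d², where s0 = √(2p̄(1−p̄)), s1 = √(pc(1−pc) + pt(1−pt)) and d = pc − pt.

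- p̄ = 0.60, so s0 = √0.48 = 0.6928
- s1 = √(0.1875 + 0.2475) = 0.6595
- n = (1.3579 + 0.5551)² / 0.09 = 40.66 per arm

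Expected evaluable patients: 84 × 0.97 / 2 = 40.74 per arm. Power = Φ[(d√n − 1.96 s0) / s1] = Φ[(0.30 × 6.383 − 1.3579) / 0.6595] = Φ(0.844) = 80.1%. At 42 per arm it is 81.3% and at 40 it is 79.3%. The stated figure reproduces for the rates given.

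**2. Power if the test is on grade 2 or higher.** The documents give no planning rates labelled grade 2+. The control rates below come from Section 1.2: 42% (minocycline trial, moderate to severe), 55% (tetracycline trial, at 4 weeks) and 62% (doxycycline trial, reactive arm, skin toxicities). The formula is the same, with 40.74 per arm. Two assumptions are shown for the effect: the plan's 30-point difference, or its relative reduction (1 − 0.45/0.75 = 40%). The last column uses the rates each cited trial reported.

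| Control rate | 30-point drop | 40% relative drop | Rates in the cited trial |
|---|---|---|---|
| 42% | 88% (42 v 12) | 36% (42 v 25.2) | 58% (42 v 20) |
| 55% | 80% (55 v 25) | 52% (55 v 33) | 96% (55 v 17) |
| 62% | 79% (62 v 32) | 61% (62 v 37.2) | 86% (62 v 29) |

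Worked example, 55 v 33: s0 = 0.7020, s1 = 0.6845, power = Φ[(0.22 × 6.383 − 1.3759) / 0.6845] = Φ(0.041) = 52%.

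**3. Can the two tests disagree?** Simulation: 200,000 trials, 41 per arm, grade 2+ nested within any grade, unstratified Mantel-Haenszel chi-square at 5%. Grade 2+ is 55% control and 17% steroid, as in the tetracycline trial. That trial's any-grade rates are not given, so the control rate is assumed to be 75% and the steroid rate is varied.

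| Any-grade rate, steroid arm | Any-severity test rejects | Grade 2+ test rejects | Tests disagree |
|---|---|---|---|
| 75% | 5% | 96% | 92% |
| 65% | 16% | 96% | 80% |
| 55% | 48% | 96% | 48% |
| 45% (planned) | 82% | 96% | 17% |

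In the reverse case (any grade 75% v 45%, grade 2+ assumed 30% in both arms), the test as written declares success in about 82% of trials and a grade 2+ test rejects in about 5%.

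**The case against.** The mismatch between Section 9.3 and the endpoint definition cannot be argued away. The case on the other side concerns what is built on it.

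- **Section 9.2 may simply be loosely worded.** It follows directly after Section 9.1, so rash incidence could mean the endpoint just defined. If so, 84 patients stands and only a label is missing. This is fair, and the documents cannot settle it.
- **The comparison rates are mixed.** The 42% is moderate to severe with no grade stated, the 55% is at 4 weeks, and the 62% is for skin toxicities in a reactive-treatment arm. That all three lie below 75% is suggestive and not proof. This stands.
- **The low power figures need an assumption the plan does not make.** Section 9.2 plans a 30-point difference, not a 40% relative reduction, and the cited trials show larger relative reductions: 52% (20 v 42), 69% (17 v 55) and 53% (29 v 62). This stands, so 36-61% is one end of a range and not an estimate.
- **The 92% disagreement is a worst case.** A trial of 61 patients reporting no difference does not establish equal rates, and disagreement falls to 17% at the planned any-grade effect. This stands as to emphasis.
- **Maximum grade will be tabulated and tested for trend.** Grade 2+ proportions will therefore be visible, and under assumed grade splits the trend test would reject in about 61-68% of trials in the equal-incidence scenario. But that test is secondary and does not address the grade 2 threshold.

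None of these points supplies a primary test of the defined endpoint.

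**Conclusion.** The concern holds. As written, the primary analysis tests a different variable from the primary endpoint, and no analysis in the plan tests the defined one. This conclusion rests on the text alone and needs no assumption.

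The size of the consequence depends on assumptions. If the steroid reduces severity and leaves incidence unchanged, the test as written has about a 5% chance of a positive result where a grade 2+ test has about 96%. If any-grade rash falls by the planned 30 points as well, the two tests disagree in about 17% of trials.

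The sample size is correct for 75% versus 45%. Whether it gives 80% power for the primary endpoint depends on what those rates describe. At the cited control rates of 42-62%, power is 79-88% for a 30-point difference and 36-61% for a 40% relative reduction. This must be fixed before analysis, because the trial's main conclusion depends on which section is followed.

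**What to change.** - **Section 9.3:** for the primary Mantel-Haenszel test, the odds ratio with its confidence interval and the homogeneity test, replace the any-severity outcome with papulopustular eruption of CTCAE v4.03 grade 2 or higher by 6 weeks. Use the same outcome in the supportive GEE model, and restate the primary objective in that section to match Section 2.1.
- **Sections 2.2, 6.3 and 9.3:** list incidence of rash of any severity as a named secondary endpoint.
- **Section 9.2:** state whether 75% and 45% are grade 2+ rates, and justify them. If they are any-grade rates, restate power at grade 2+ rates, with the assumed effect given explicitly.

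**Cost:** a wording amendment. Maximum grade is already due to be tabulated, so no new data are needed. If 75% and 45% prove to be any-grade rates, the stated power may become less favourable. For example, 55% versus 33% would need 79 per arm for 80% power, against the 42 planned. The sponsor would then have to accept and report the lower power or revisit the sample size.
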